subscore of the Constant-Murley score remained significantly improved. They were unable to associate the grade of OA to pain relief following IACSI.

This study differs dramatically from clinical practice, where IACSI is normally administered as a single injection. Repeat injections are often delayed, with some surgeons recommending a three month break between injections. Presently, there is an evidence gap with respect to evidence of the effectiveness of single-injection IACSI on clinical and patient-reported outcomes in patients with glenohumeral OA.

5. Specific Aims

To address this deficit in the literature, there are two specific aims:

1. Assess the effectiveness of IACSI in patients with primary osteoarthritis in the shoulder. This will be determined through three patient-reported outcomes measures:
 - ASES (American Shoulder & Elbow Surgeon) score improvement > 20.9 points⁸
 - VAS (Visual Analog Scale) pain score improvement > 1.4 points
 - SST (Simple Shoulder Test) score improvement > 2.4 points
2. Assess clinical and radiographic predictors of success (outlined below) in patients who elect to receive IACSI as treatment for primary osteoarthritis in the shoulder.
 - Clinical
 - Duration of Symptoms
 - Location of pain (Anatomic Diagram, Figure 1)
 - Pain diagrams will be analyzed using a computer overlay protocol and analyzed in a binary matter according to region. Image software (NIH, Bethesda, MD) will be used. Proportions of the patients responding to injection in each anatomic region and groups of regions will be calculated. 95% confidence intervals will be determined.¹
 - History of prior injection
 - Range of motion (Forward elevation in the scapular plane, ER at 0° abduction, IR at 0° abduction)
 - Standardized pain and function scores (VAS pain, SST, ASES)
 - Prior analgesia (OTC, Narcotic)
 - Initial response to anesthetic component (VAS 5-10 min post-injection)
 - Radiographic
 - Joint space narrowing (measured)
 - Subluxation
 - Walch classification
 - Subchondral cysts
 - Samilson & Prieto Radiological Classification
 - Mild Arthrosis: inferior humeral and/or glenoid exostosis < 3mm in height

- Moderate Arthrosis: inferior humeral and/or glenoid exostosis measuring 3mm to 7mm slight gleno-humeral irregularity
- Severe Arthrosis: inferior humeral and/or glenoid exostosis measuring > 7mm gleno-humeral joint narrowing and sclerosis

6. Research Plan

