Subjects: Five hundred patients, both male and female, age 18-100 years, with a diagnosis of symptomatic primary osteoarthritis of the shoulder will be recruited from the patient population seeking treatment at the Orthopaedics Sports Medicine Institute. Subjects enrolled into the study will be those who have failed previous treatment including over-the-counter analgesics and activity modification, and have elected to receive a medically-indicated, ultrasound-guided IACSI in the shoulder. Two or three plain film views of the shoulder (including a Grashey and axillary lateral) obtained in accordance with standard of care prior to enrollment in the study will be reviewed. Once written informed consent has been obtained, subjects will complete the pre-procedural pain chart (Figure 1), ASES, VAS pain (at rest, with activity, at night), and SST scores. Upon completion of all outcomes measures, the ultrasound-guided IACSI (5cc of 1% lidocaine, 2cc of depomedrol (40mg/mL)) will be administered. Subjects will be asked to repeat the VAS pain score (at rest) 5-10 minutes following administration of the injection to assess the response to the anesthetic component of the injection. Upon conclusion of the visit, no clinical follow-up appointment will be scheduled, and subjects will be instructed to follow-up with their physician as needed; this is in accordance with standard of care for this patient population.

MRN: _____
 Date: _____
 Diagnosis: _____
 Injection: _____
 Pain: Pre: _____ post: _____
 Global: Yes No

Please shade in the areas where you are feeling pain now.
 Please mark with a dark circle (●) the areas where the pain is the worst.

(Figure 1: Pre-procedural pain chart, anatomic diagram)

Subjects will be contacted via email through the REDCap survey function or a phone call at two weeks, one month, two months, three months, and six months following the injection to complete the ASES, VAS pain (at rest, with activity, at night), and SST scores. If an email survey is not completed in REDCap, a reminder email will be sent every two days, up to two

times. If, after the final email reminder, the REDCap survey is still incomplete, a member of the study staff will call the subject and complete the survey via telephone call.

Exclusion Criteria: Patients will be excluded from the study for any of the following reasons:

- Post traumatic osteoarthritis
- Inflammatory osteoarthritis
- Imaging confirmed rotator cuff tear
- Prior ipsilateral shoulder surgery

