- Memory loss or inability to complete study measures
- History of allergy to injection medications
- Diabetic patients with patient-reported fasting blood glucose >200
- Prior injection in the ipsilateral shoulder within three months

Data Collection: The following data points and information will be collected for later analysis:

- Patient name
- MRN
- Gender
- Date of birth
- E-mail address
- Telephone number
- Location of pain (pre-procedural pain chart)
- Duration of symptoms
- History of prior IACSI in ipsilateral shoulder
- Prior analgesia
- Shoulder Range of Motion (Forward elevation, External rotation, Internal rotation)
- Radiographic findings
- Date of IACSI
- Date of each follow-up survey
- Results of each standardized pain and function survey

Confidentiality: Once all enrolled subject data is collected, subject PHI will be removed and the data will be maintained by using assigned research identification numbers that uniquely identify each individual. Date of birth will be converted to age, and dates will also be converted to time frames. Coded data will be stored on a secure online database such as REDCap and an Excel spreadsheet on a password protected computer within the Department of Orthopaedics and Rehabilitation. Data will be converted to a SPSS file for analysis which will also be stored on a secure department server. Data will be used only in aggregate and no identifying characteristics of individuals will be published or presented. Only the study team members will have access to these files. After the study is completed, local data will be stored with other completed research studies in a secured storage room until the appropriate time when the research files may be purged according to university policy.

Data Analysis:

Each patient-reported outcome measure will be assessed at each time point pre- and post-injection and grouped according to the grade of shoulder osteoarthritis. Groups will be compared using a one-way ANOVA analysis. Groups with a response to injection (VAS score improvements greater than the minimal clinically important difference) will be compared to those without a significant response. Single multi-level regression analysis will be performed to assess for clinical and radiographic risk factors outlined in Aim Two that may predict corticosteroid injection failure.

7. Possible Discomforts and Risks

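### Does the responder split need a change because the plan names neither the VAS item nor the follow-up visit that defines response?

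*Combined protocol and SAP*

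**What the plan says.** Data Analysis (section 6) separates patients whose response is "VAS score improvements greater than the minimal clinically important difference" from the rest. Aim 1 in section 5 supplies the threshold, "VAS (Visual Analog Scale) pain score improvement > 1.4 points", with no item or time attached.

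The follow-up paragraph of section 6 contacts patients at "two weeks, one month, two months, three months, and six months following the injection" and asks them "to complete the ASES, VAS pain (at rest, with activity, at night), and SST scores". Each follow-up therefore yields three VAS change scores. The one place where a single item is singled out is the request to "repeat the VAS pain score (at rest) 5-10 minutes following administration of the injection". That reading gauges the anesthetic, and Aim 2 lists it as a predictor.

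Three other sentences bear on the point:
- Data Analysis opens with "Each patient-reported outcome measure will be assessed at each time point pre- and post-injection", in a sentence about grouping by osteoarthritis grade.
- It ends with "Single multi-level regression analysis will be performed to assess for clinical and radiographic risk factors outlined in Aim Two", where the outcome is injection failure.
- Under Aim 2, for the pain diagrams, "Proportions of the patients responding to injection in each anatomic region and groups of regions will be calculated".

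**The concern.** Taken literally, the rule is incomplete. A patient may improve by more than 1.4 points on activity pain at one month and not on rest pain at three months. The protocol does not say whether that patient is a responder.

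The split feeds the comparison of responders with non-responders and may also feed the pain-diagram proportions and the failure regression. If the item and visit were settled after looking at the results, the responder rate and the list of predictors could both reflect that choice. Section 8 of the protocol says the findings may help providers predict response, so an outcome with many possible definitions looks like a serious weakness.

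There is also a floor. Someone who starts at 1.4 or below on the chosen item can never count as a responder on it, and the eligibility criteria set no minimum pain score.

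**Working it through.** **Count of definitions.** Items: 3 (rest, activity, night). Follow-ups: 5 (2 weeks; 1, 2, 3 and 6 months). 3 x 5 = 15. This is a minimum: adding the mean of the three items gives 4 x 5 = 20, and any-visit or sustained-response rules add more. Naming only the item leaves 5; naming only the visit leaves 3. If the split is made at every visit, at least 3 definitions remain.

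**How far the undefined variable reaches.** Only the responder comparison is tied to VAS in the text. The pain-diagram sentence gives no VAS rule, and the chart in Figure 1 has its own pre and post pain entries and a yes/no global field. The regression concerns injection failure, and Aim 1 gives thresholds for three measures (ASES, VAS, SST). Either analysis may use the VAS split, but the protocol does not say so.

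**Illustrative size.** The protocol gives no SD, correlation or significance level, so these are assumed: normal scores, SD 2.5, floor ignored, and all correlations 0.5 to 0.9. The mean change is 6.25 - 4.4 = 1.85, the one-month result of the earlier three-injection study described in section 4. Let rb be the correlation of baseline with follow-up and rf that between follow-ups (rf at least rb).

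- SD of change = 2.5 x sqrt(2(1 - rb)): 2.50, 1.94 and 1.12 at rb = 0.5, 0.7 and 0.9.
- Responder rate = Φ((1.85 - 1.4)/SD of change): 0.571, 0.592 and 0.656.
- Correlation between two change scores: the item correlation (two items, same visit); (1 - 2rb + rf)/(2(1 - rb)) (two visits, same item); the product of the two (both differ).
- Patients classified differently = p1 + p2 - 2 x P(responder on both).

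| Definitions compared | Classified differently |
|---|---|
| Two items, same visit | 13% to 33% |
| Two visits, same item | 14% to 33% |
| Item and visit both differ | 20% to 41% |

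**Checking the illustration against section 4.** The figures apply 1.85 at every visit, yet the same earlier study had no significant difference left at three or six months. With a later mean change of 0, the later responder rate is 1 - Φ(1.4/SD of change): 0.288 at rb = 0.5 and 0.105 at rb = 0.9. Two-visit disagreement then runs from 29% (rb 0.5, rf 0.9) to 57% (rb and rf 0.9).

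Most of that is the effect wearing off. The rates alone differ by 0.571 - 0.288 = 0.283 and by 0.656 - 0.105 = 0.551. Disagreement of this kind is a finding to report by visit.

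**False positives.** For a null predictor at an assumed two-sided 5% level, with equal correlations between tests of 0.9 to 0.5, the chance of at least one positive result is 8% to 13% over 3 definitions, 10% to 18% over 5, and 14% to 36% over 15. The score model above implies lower test correlations (0.15 to 0.71) and gives 28% to 48% over 15. All of these describe an analyst who tries every definition and reports the favourable one. The protocol does not plan that.

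**The case for a change.** The case for a change is straightforward. The missing item and visit can be read directly from the text, and the remedy is a few sentences with no new data. The usual escapes are incomplete: the phrase about each time point belongs to the by-grade comparison, the word multi-level is not explained, and either reading still leaves the item open. A predictor study gains credibility when its outcome is fixed in advance, and an observational design does not remove that point.

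The gap, the count and the value of early definition all stand. What does not stand is the step from there to a defect in the plan:
- Any sensible item and visit would serve if named first, so the objection is to silence and not to a stated method.
- The reach to the pain diagrams and the regression is inferred.
- The percentages rest on assumed inputs, and the two-visit range shifts once section 4 is taken at its word.
- The floor argument has no item-level baseline data behind it. The one earlier study cited reports one-month improvement in both night and activity pain, so those two items at least moved the same way.
- Tying Aim 1 to one visit, or relabelling the by-grade ANOVAs, would not follow from an unnamed VAS item.

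**Conclusion.** No change to the plan is called for. The protocol leaves at least 15 responder definitions open, or at least three on an every-visit reading, and an analyst has to fill that gap. It can be filled sensibly from data already planned: one named item at one visit, each item at each visit, or a model over all visits. In a single-arm cohort with no declared primary endpoint or significance level, leaving this unwritten breaches no error-rate claim and biases no treatment comparison.

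The possible effect is not negligible. The illustrations put disagreement at about 13% to 41% with equal mean change, and at 29% to 57% between two visits if the effect fades. These depend on an assumed SD of 2.5, assumed correlations of 0.5 to 0.9 and a mean borrowed from a different injection regimen, so they show scale only. The conclusion rests on the analysts fixing the definition without reference to the results and stating it when they report. If a report gave a single item and visit without a reason, its predictor findings would deserve less weight.

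### Age and sex are collected but are missing from the Aim 2 factors that define the regression, and the comparison across arthritis grades is an unadjusted one-way ANOVA

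*Combined protocol and SAP*

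**What the plan says.** Section 5, Aim 2 sets the task: "Assess clinical and radiographic predictors of success (outlined below) in patients who elect to receive IACSI". The list that follows has seven clinical items (symptom duration, pain location, earlier injection, range of motion, baseline scores, earlier analgesia, response to the anesthetic) and five radiographic ones (joint space, subluxation, Walch type, cysts, Samilson-Prieto grade). Age and sex are not on it.

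Section 6, Data Analysis, plans a regression "to assess for clinical and radiographic risk factors outlined in Aim Two that may predict corticosteroid injection failure". No other covariate is named. For outcomes grouped by arthritis grade, the same paragraph says "Groups will be compared using a one-way ANOVA analysis".

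Section 6, Data Collection, opens with "The following data points and information will be collected for later analysis" and lists gender and date of birth. Under Confidentiality, "Date of birth will be converted to age", so age survives de-identification.

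The Subjects paragraph admits both sexes from 18 to 100 years. All participants "have elected to receive a medically-indicated, ultrasound-guided IACSI in the shoulder".

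**The concern.** The study will hold two basic patient characteristics to which the plan gives no analytic role. This touches both analyses.

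- **Regression.** Prediction is the purpose of Aim 2. A model restricted to the listed factors passes over two candidates that cost nothing to include, and may predict somewhat less well than the data allow.
- **Comparison across grades.** Grade is not randomised, eligibility restricts neither age nor sex, and everyone chose the injection. If age or sex is related both to grade and to outcome, mean outcome will differ between grades partly for that reason, and a one-way ANOVA cannot show how much. The protocol itself raises the question of grade: of the one earlier steroid study, section 4 says "They were unable to associate the grade of OA to pain relief following IACSI". If this study finds a link, readers will ask whether it reflects age.

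**Working it through.** **Text check.** The regression sentence points to the Aim 2 list. Of its 7 + 5 = 12 items, none is age or sex. Both are in the Data Collection list. A one-way ANOVA has a single factor and no covariates. The omission is therefore confirmed in both analyses as written.

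**Size.** The documents give 500 patients and a VAS criterion ("VAS (Visual Analog Scale) pain score improvement > 1.4 points"). They give no significance level, SD, response rate, or association of age or sex with anything, so there is no planned figure to reproduce. Everything below is illustrative.

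Assumptions: all 500 analysed; three equal grades (mild, moderate, severe) cut from a normal latent severity; no grade effect beyond age; two-sided 5% level; age-grade (latent) correlation *r* = 0.2-0.3; age-outcome correlation *b* = 0.1-0.2.

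1. The mean of the top third of a standard normal is 1.091, so top and bottom thirds differ by 2 × 1.091 = 2.18 SD.
2. Age-driven gap in outcome, severe versus mild: *d* = 2.18 × *r* × *b*.
3. With grade means at -*d*/2, 0 and +*d*/2, the noncentrality is λ = (500/3) × *d*²/2.
4. Detection rate: the probability that a noncentral F with 2 and 497 degrees of freedom exceeds its 5% critical value.

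| *r* | *b* | *d* (SD) | λ | ANOVA detects a difference |
|---|---|---|---|---|
| 0.2 | 0.1 | 0.044 | 0.16 | 6.2% |
| 0.3 | 0.1 | 0.065 | 0.36 | 7.8% |
| 0.2 | 0.2 | 0.087 | 0.63 | 10.1% |
| 0.3 | 0.2 | 0.131 | 1.43 | 17.1% |

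Simulation agrees: about 6-18% unadjusted and 5-6% with age and sex as covariates. The adjusted figure is the assumed 5% apart from simulation noise. If either association is zero, the unadjusted rate is also about 5%.

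**On the VAS scale.** At an assumed SD of change of 2-3 points, *d* runs from 0.044 × 2 = 0.09 to 0.131 × 3 = 0.39 points, which is 6% to 28% of 1.4. That threshold is for improvement within a patient, so it serves here only as a yardstick.

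**Sex.** With grades shifted 0.2-0.5 SD between the sexes and an outcome difference of 0.2-0.4 SD, the simulated ANOVA detected a difference in 5-12% of studies, against 5% adjusted.

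**Sensitivity to the assumptions.** With an outcome slope of 0.3 SD per SD of age and an age gap of 1.0 SD between mild and severe, *d* = 0.30 SD. At 167 per grade the ANOVA would detect it in 69% of studies. Even then the gap is 0.30 × 2.5 = 0.75 points at an SD of 2.5.

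**Regression.** Simulated as a logistic model with 50% response, 12 factors and two true predictors unrelated to age, adding age and sex changed the AUC by +0.001 to +0.008 at an age odds ratio of 1.25 per SD, by +0.008 to +0.028 at 1.5, and by -0.002 to -0.003 if neither matters.

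**The case against.** The strongest reply is that the ANOVA makes no error. It tests whether grade means are equal. If age drives both grade and outcome, the means do differ, and the 6-18% is power to detect a real unadjusted difference. A reader might infer from those rates that the planned test has an inflated type I error. The documents do not support that: they never state that the target is the effect of grade independent of age and sex, and title and aims speak of prediction. In prediction, a factor that carries age information is still a valid predictor. This part of the reply stands.

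A second reply is that nothing forbids using age and sex: both are among the items collected for analysis, and the regression sentence does not say that only the Aim 2 factors may enter. That also stands, so the plan cannot be said to exclude them. But the same list covers name, record number and telephone number, so it assigns no analytic role. Variables added after results are seen are a discretionary choice.

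A third reply is that the whole magnitude rests on assumed associations, and that the expected gain in the regression is slight and could be a small loss. That is correct and limits how much weight the point can carry. It does not remove the omission, or the fact that the planned ANOVA cannot say whether a grade difference goes beyond age and sex.

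**Conclusion.** The point holds as a cheap improvement that the sponsor could make, not as a flaw that invalidates either analysis. Under the plan as written, two baseline variables already held are left out of the prediction model and of the comparison across grades, so a grade difference could not be separated from age or sex.

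The size is unknown. It is tempting to call the effect modest, or large, but documents that report no association support neither: the assumed inputs above span rates from about 5% to 69%. On the central illustration, adjustment moves the detection rate of an age-driven difference from 6-18% to 5-6%, and the gap of 0.04-0.13 SD would not approach the VAS threshold. The risk is a statistically significant grade difference read as an effect of grade itself, not a clinically large spurious one. If age and sex are unrelated to grade or to outcome, the unadjusted comparison is not distorted.

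**What to change.** Add age (continuous) and sex to the Aim 2 clinical candidates and enter both in the regression. Report the comparison across grades adjusted for age and sex (ANCOVA) beside the planned one-way ANOVA, so that the unadjusted result is kept and the two can be compared.

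The cost is two degrees of freedom out of 500 patients, with no new data and no change in sample size. There is a possible price in power for the adjusted comparison. If age and sex prove unrelated to response and the true grade effect is 0.17 SD per step, simulated power (about 80% unadjusted) falls by 1.4-1.6 points at an age-grade correlation of 0.2, 3.4-3.6 at 0.3 and 6.3-6.5 at 0.4, so roughly 2-6 points. If age and grade are unrelated, nothing measurable is lost.
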